#### **7.1.3 Oral hygiene**

Oral hygiene will be performed every 12 h and oral moistening every 2 hours based on policy of the ICU.

## **8.0 Data Collection**

All data will be collected non-invasively and will already be a part of clinical data obtained in usual ICU care at the bedside or in the medical record. No additional data will be obtained beyond that which is obtained by bedside observation and from the electronic medical record.

**Baseline:** Age, gender, height, weight, race, active medical problems at the time of intubation, active comorbidities complicating intubation, indication for intubation, whether it is a reintubation, whether the face was soiled during the intubation

**Periprocedural:** Depth of tube as measured at lip line and position in mouth (ie 22 cm at the lip, midline) at time of securement

**In-Hospital Outcomes:** days on mechanical ventilator, ICU mortality, mortality for ventilator free days, oral mucosa assessment, facial skin integrity assessment, frequency of endotracheal tube repositioning, endotracheal tube dislodgements – defined as either complete

Principal Investigator: [name], ACNP-BC

Study Title: Adhesive Versus Endotracheal Tube Fastener

Institution: Vanderbilt University Medical Center

Version Date: 3/21/2018

dislodgement of the endotracheal tube (i.e. accidental extubation) or needing to reposition the endotracheal tube more than 1 cm (i.e. need to pull ETT back 2+ cm or move it down 2+ cm).

The following study endpoints will be collected if they occur anytime between randomization and the earlier of death, hospital discharge, tracheostomy placement, or 48 hours after extubation: lip ulcers, facial skin tears, tube dislodgement, and ventilator associated pneumonia.

Ventilator-free days will be collected from the time of randomization through study day 28. In order to get credit for a ventilator-free day, a patient must be both alive and free of mechanical ventilation. Patients who are extubated and reintubated will only be credited with being free of mechanical ventilation for days after the last extubation. Patients who die before study day 28, regardless of whether or not they ever achieved unassisted breathing, will be assigned zero ventilator-free days. Patients who are still on the ventilator at study day 28 will also receive zero ventilator-free days. Patients who are discharged from the hospital prior to study day 28 free of mechanical ventilation will be assumed to remain free of mechanical ventilation through study day 28. Patients who are discharged from the hospital prior to day 28 on mechanical ventilation will try to be followed at the discharge location for date of extubation – however, if the date is not able to be obtained, they will be assumed to have zero ventilator free days in the analysis.

## **9.0 Risk and Benefits**

In patients for whom the treating team has decided endotracheal intubation is required, there are currently no established risks or benefits to endotracheal tube securement with adhesive tape or endotracheal tube fastener. Additionally, previous studies of endotracheal tube securement of critically ill adults suggest that in routine care, respiratory therapists arbitrarily decide to use adhesive tape or endotracheal tube fastener. At this time, there is no reason to believe that participation in this study would expose patients to greater medical risks or benefits than those experienced by critically ill patients requiring endotracheal intubation and securement as a part of routine care. The greater benefit of the study would be to improve understanding of safe and effective endotracheal tube securement for critically ill patients.

A potential risk to patients participating in this study involves the collection of protected health information (PHI). In order to limit the associated risks, the minimum amount of PHI necessary for study conduct will be collected. After collection, the data will be stored in a secure online database (REDCap) only accessible by the investigators. After publication, a de-identified database will be generated to protect participant privacy.

## **10.0 Safety Monitoring and Adverse Events:**

### **10.1 Safety Monitoring**

This study will take place in the environment of the intensive care unit. At the time of the study intervention, the patient will have in the room a critical care nurse and respiratory therapist.

Principal Investigator: [name], ACNP-BC

Study Title: Adhesive Versus Endotracheal Tube Fastener

Institution: Vanderbilt University Medical Center

Version Date: 3/21/2018

Additionally, there will be continuous invasive or non-invasive monitoring. Additionally, study personnel will readily be available to answer questions at any time during the study course. Even after randomization if any healthcare provider participating in the endotracheal tube securement study believes that the study interventions cannot be performed for the safe performance of the procedure or the safety of the patient, the study intervention is halted and the patient has the endotracheal tube secured in the manner which the clinical team judges to be safest.

## **10.2 Adverse Events**

An adverse event is defined as any untoward medical occurrence in a clinical investigation participant administered an intervention that does not necessarily have to have a causal relationship with this treatment. An adverse event therefore can be any unfavorable and unintended sign, symptom, or disease temporally associated with the use of an intervention, whether or not the incident is considered related to the intervention.

A serious adverse event (SAE) is defined as any unexpected and untoward medical occurrence that is probably or possibly related to the study and meets any of the following criteria:

- a. Results in death
- b. Is life-threatening (defined as an event in which the participant was at risk of death at the time of the event and NOT an event that hypothetically might have caused death if it would have been more severe)
- c. Requires inpatient hospitalization
- d. Prolongs an existing hospitalization
- e. Results in persistent or significant disability or incapacity
- f. Results in a congenital anomaly or birth defect
- g. Important medical event that requires an intervention to prevent any of a-f above.

The Principal Investigator will be responsible for overseeing the safety of this trial on a daily basis. She will be available at any time for questions from the bedside nurses or respiratory therapists, who will also be monitoring the patients continuously for adverse events and serious adverse events. Serious and unexpected adverse events associated with study interventions will be recorded in a case report form in the study record and reported to the IRB within 10 business days.

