## **2.0 Background**

### **2.1 Complications of endotracheal tube securement**

Effective endotracheal tube securement is imperative in providing safe mechanical ventilation. Various techniques have been utilized to ensure endotracheal tube stabilization in order to maintain a patent airway and prevent complications. One common complication of endotracheal tube securement is lip ulcers. The development of lip ulcers is not rare and is associated with increased financial burden and potentially increased length of stay. Endotracheal tube dislodgement is another common complication of tube securement. It is imperative for the tube to be correctly positioned to maintain optimum airway passage and promote effective mechanical ventilation. If the tube is not secured correctly, it can become dislodged which may result in unplanned extubation, bronchospasm, and tracheal injury. Additionally, endotracheal intubation and mechanical ventilation is associated with ventilator associated pneumonia. Proper oral hygiene is essential in decreasing the incidence of ventilator associated pneumonia. Utilizing an endotracheal tube securement technique that enables providers to perform oral hygiene is imperative. It is thought that modifying endotracheal tube securement technique could reduce these complications.

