## **12.0 Statistical Considerations**

### **12.1 Sample Size Determination**

We estimated the incidences of tube dislodgement to be 20 per 1000 ventilator days and the incidence of lip ulcer development in the previous 12 months was 1.1 per 1000 ventilator days. Using the sum of these overall incidences of 21.1 per 1000 ventilator days and a standard deviation of 15 per 1000 ventilator days, we calculated a need for 142 patients in each arm to detect a clinically meaningful change of 5 episodes per 1000 ventilator days with 80% power at a two-sided alpha level of 0.05. We plan to enroll 500 patients which would allow for a 5.6% dropout or loss to follow-up rate. We used PS software to calculate the sample size.

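### The SAE definition in section 10.2 requires the event to be unexpected, so a serious accidental extubation, which the protocol foresees, can be left out of SAE recording and reporting

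*Combined protocol and SAP*

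**What the plan says.** Section 10.2 first defines an adverse event broadly, as any untoward occurrence "whether or not the incident is considered related to the intervention". It then narrows the serious category: "A serious adverse event (SAE) is defined as any unexpected and untoward medical occurrence that is probably or possibly related to the study", with at least one of criteria a-g (death, life-threatening, and so on) also required. The recording rule carries the same limit: "Serious and unexpected adverse events associated with study interventions will be recorded in a case report form in the study record", with a report to the IRB within 10 business days.

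Elsewhere the protocol treats loss of tube position as a known problem. Section 2.1 says: "Endotracheal tube dislodgement is another common complication of tube securement", and, of a badly secured tube, that "it can become dislodged which may result in unplanned extubation, bronchospasm, and tracheal injury". Section 12.1 builds a rate into the sample size: "We estimated the incidences of tube dislodgement to be 20 per 1000 ventilator days". Section 1.0 makes dislodgement a component of the primary composite and a secondary endpoint in its own right. Section 8.0 defines dislodgement to include both accidental extubation and repositioning of more than 1 cm.

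Section 9.0 points the other way. It says that "there are currently no established risks or benefits to endotracheal tube securement with adhesive tape or endotracheal tube fastener". No section defines *unexpected*, lists expected events, or says how an endpoint event that meets a-g is to be handled.

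**The concern.** Seriousness, expectedness and relatedness are three separate judgements. Section 10.2 merges them, so an event that causes death or threatens life is not an SAE if someone regards it as expected. The event most exposed to that rule is accidental extubation, a main foreseeable harm of the devices being compared and one the protocol itself anticipates.

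If the rule is applied that way, the trial could report few or no SAEs although serious tube losses had occurred, and the SAE tables would not show whether they differed between tape and fastener. The setting adds weight. Consent is to be waived on a minimal-risk argument. Section 10.2 places daily safety oversight with the principal investigator, and the documents describe no monitoring board or interim safety review. No blinding is described and the device is visible at the bedside, so an undefined term would be judged with knowledge of the arm.

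**Working it through.** The point rests on the text, so the main check sets the provisions side by side.

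**Step 1: conditions for an SAE (section 10.2).** All three must hold:
1. the event is unexpected;
2. it is probably or possibly related to the study;
3. it meets at least one of a-g.

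**Step 2: apply them to an accidental extubation that threatens life or ends in death.**
- Condition 3 is met through criterion a or b.
- Condition 2 is readily met, since a tube lost through failure of the securement under study is at least possibly related.
- Condition 1 is unclear. Sections 2.1, 8.0 and 12.1 foresee the event, which supports calling it expected. Section 9.0 recognises no established risk, and section 2.1 does not mention arrest or death, which supports calling a fatal outcome unexpected.

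Classification therefore depends on condition 1 alone, and the protocol gives no rule for deciding it.

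**Step 3: does another record fill the gap?**

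| Source | What it captures | What it does not list |
|---|---|---|
| Dislodgement endpoint (1.0, 8.0) | Accidental extubation and repositioning of more than 1 cm, as one endpoint | Severity, consequence, attribution |
| ICU mortality (8.0) | Death | Any link to a preceding tube loss |
| Ventilator-free days (8.0) | Death before day 28; days after the last extubation if reintubated | Cause of death or of reintubation |
| Follow-up after discontinuation (11.0) | Patients who discontinue for a safety reason, or who leave for another reason but also have a safety event | Patients who stay in the study |

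Cross-tabulating dislodgement with death would not show whether one led to the other, and it would miss life-threatening events that the patient survived.

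**Step 4: scale.** The plan states no figure on this point, so there is none to reproduce. Inputs are 500 patients and 20 dislodgements per 1,000 ventilator days (both from 12.1). Mean ventilator days per patient, *d*, is **assumed**, because the documents do not give it.

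Expected dislodgements = 500 × *d* × 20/1000 = 10 × *d*

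| Assumed *d* | Ventilator days | Dislodgements of any kind |
|---|---|---|
| 3 | 1,500 | 30 |
| 5 | 2,500 | 50 |
| 7 | 3,500 | 70 |
| 10 | 5,000 | 100 |

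These counts include repositioning. The share that are accidental extubations is not given. At *d* = 5, an assumed share of 5% to 50% gives 50 × 0.05 = 2.5 to 50 × 0.50 = 25. The share meeting a-g is not given either. The figures show that dislodgement is anticipated. They do not count lost SAEs.

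**The case against.** A reader might infer that a fatal accidental extubation can never be an SAE under this protocol. The text does not go that far. *Unexpected* is undefined, no list of expected events exists, and endpoint events are not exempted from SAE reporting. An investigator could properly call a death unexpected in severity and cite section 9.0 in support. This stands. The documents support only that the event can be left out.

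A reader might also blame the relatedness condition. For this event it excludes nothing, since the bar is only a possible relation. It matters for other serious events judged unrelated.

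It is also tempting to call section 10.2 self-contradictory, because it refers to serious and unexpected events after already placing expectedness inside the definition. That is redundant wording. Both sentences impose the same limit.

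Nor are the events lost altogether. Dislodgement is an endpoint, ICU mortality is collected, and bedside staff watch for adverse events under a definition with no expectedness condition. The case report form is not in the documents, so it may already separate accidental extubation from repositioning. This narrows the gap but does not close it, because the listed data include no severity or attribution field and only serious and unexpected events are explicitly sent to a case report form.

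Finally, recording every a-g event in ventilated ICU patients would sweep in deaths and prolonged stays with no link to securement, in a trial of two routine methods. That objection is fair, and it is why recording should be confined to securement- and airway-related events.

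**Conclusion.** The concern holds in a limited form. Applied as written, section 10.2 permits a life-threatening or fatal accidental extubation to be left out of SAE recording and IRB reporting, because the protocol foresees the event, requires SAEs to be unexpected and does not say what that means. What is at risk is the classification, grading and comparison by arm of serious securement failures. The count of dislodgements is not at risk.

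The number of events affected cannot be derived from the documents. The 30 to 100 dislodgements of any kind rest on the planned rate, full enrolment of 500 and an assumed 3 to 10 ventilator days per patient, and the serious share is unknown. The sample size and the primary analysis are unaffected. The change should be made because it is cheap and because safety oversight here relies heavily on this section.

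**What to change.** In section 10.2:

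1. Define seriousness by criteria a-g alone, and assess relatedness and expectedness as separate fields.
2. Record on the case report form every securement- or airway-related event that meets a-g, whether or not it was expected. State that this includes dislodgements and skin events already counted as endpoints.
3. Report these events by arm, with accidental extubation shown separately from repositioning.
4. Define *unexpected* by nature, severity or frequency.
5. Keep serious, unexpected and related as the trigger for the 10-business-day IRB report.

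The cost is protocol wording, a few form fields and somewhat more events to record. Confining the rule to securement- and airway-related events keeps that workload small and leaves the IRB trigger as it is.

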## **11.0 Study Withdrawal/Discontinuation**

Patients can be withdrawn from study participation in the following circumstances:

- The investigator or medical team decides that the patient should be withdrawn for safety considerations.

- There is a significant protocol violation in the judgment of the PI.

The reason and date of every withdrawal will be recorded in the patient study records. Follow-up will be performed for all patients who discontinue due to an adverse event or any other safety parameter. Follow-up will also be performed for all patients who end participation in the protocol for another reason, but who also have an adverse event or other safety parameter that could have led to discontinuation. Follow-up will be conducted until the condition has resolved, until diagnosis of the adverse event or safety parameter is deemed chronic and stable, or as long as clinically appropriate. This follow-up will be documented in the patient study record as well.

## **12.0 Statistical Considerations**

### **12.1 Sample Size Determination**

We estimated the incidences of tube dislodgement to be 20 per 1000 ventilator days and the incidence of lip ulcer development in the previous 12 months was 1.1 per 1000 ventilator days. Using the sum of these overall incidences of 21.1 per 1000 ventilator days and a standard deviation of 15 per 1000 ventilator days, we calculated a need for 142 patients in each arm to detect a clinically meaningful change of 5 episodes per 1000 ventilator days with 80% power at a two-sided alpha level of 0.05. We plan to enroll 500 patients which would allow for a 5.6% dropout or loss to follow-up rate. We used PS software to calculate the sample size.

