- Composite of any of: presence of lip ulcer, endotracheal tube dislodgement, or facial skin tears from the time of randomization to the earlier of death or 48 hours after extubation

Secondary Endpoints:

- Presence of Lip Ulcer
- Endotracheal tube dislodgement
- Ventilator associated pneumonia incidence

- Facial skin tears
- Ventilator-free days

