#### **12.4 Primary Analyses**

The primary endpoint will be the continuous variable of incidences of lip ulcers, tube dislodgement, or ventilator associated pneumonia per 1,000 ventilator days. The differences between the two groups will be compared using the Mann-Whitney U test. All other comparisons will be considered secondary analyses.

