#### **14.0 Follow-up and Record Retention**

Patients will be followed after enrollment for 28 days or until hospital discharge, whichever occurs first. Data collected from the medical record will be entered into the secure online database REDCap. Hard copies of the data collection sheet completed at the time of the airway management event will be stored in a locked room until after the completion of enrollment and data cleaning. Once data are verified and the database is locked, all hard copies of data collection forms will be destroyed. All data will be maintained in the secure online database REDCap until the time of study publication. At the time of publication, a de-identified version of the database will be generated.

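### The SD of 15 per 1,000 ventilator days is too small for per-patient event rates, so 142 per arm does not give the stated 80% power, and under Poisson variation neither do 500 patients

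*Combined protocol and SAP*

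**What the plan says.** Section 12.1 adds a dislodgement rate ("We estimated the incidences of tube dislodgement to be 20 per 1000 ventilator days") and a lip ulcer rate of 1.1 to reach 21.1 per 1,000. It then proceeds "Using the sum of these overall incidences of 21.1 per 1000 ventilator days and a standard deviation of 15 per 1000 ventilator days", and concludes: "we calculated a need for 142 patients in each arm to detect a clinically meaningful change of 5 episodes per 1000 ventilator days". The target there is a power of 80%, testing two-sided at alpha 0.05. It plans 500 patients and describes this as allowing for 5.6% dropout.

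Section 12.4 sets the analysis variable: "The primary endpoint will be the continuous variable of incidences of lip ulcers, tube dislodgement, or ventilator associated pneumonia per 1,000 ventilator days". The arms are compared by Mann-Whitney U test. Section 1.0 instead defines the primary endpoint as a yes/no composite of lip ulcer, dislodgement or facial skin tear.

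No section gives an expected number of ventilator days per patient or a source for the SD.

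**The concern.** The sample size counts patients, so the SD must describe how the event rate varies from patient to patient. Such rates are coarse: no event gives 0, and one event in 10 ventilator days gives 100 per 1,000. A mean of 21.1 with an SD of only 15 is hard to obtain from values like these. An SD of that size looks more like the spread of rates pooled over a unit or a period. If that is its origin, it cannot be combined with patients as the sampling unit.

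The 80% figure is the only stated justification for the sample size. If it is wrong and the rate endpoint is kept, a null result could be read as evidence against a difference the protocol itself regards as clinically meaningful, although the trial had little chance of detecting it.

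**Working it through.** **Inputs from Section 12.1:** control rate 21.1 per 1,000 ventilator days, difference 5 (so 16.1 in the better arm), SD 15, two-sided alpha 0.05, power 80%, 142 per arm, 500 planned, 5.6% dropout. After dropout, 500 × 0.944 = 472, or 236 per arm. **Assumed, because the documents give no figure:** 28, 10 and 5 ventilator days per patient.

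**1. The plan's own figure.** n = 2 × 15² × (1.960 + 0.842)² / 5² = 141.3, i.e. 142 per arm. It is reproduced, so 15 was used as a between-patient SD.

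**2. SD under Poisson counts.** SD = 1000 × √(0.0211/T), with T the ventilator days per patient:
- T = 28: 27.5
- T = 10: 45.9
- T = 5: 65.0

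An SD of 15 would need T = 0.0211/0.015² = 93.8 days.

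**3. Power for 21.1 versus 16.1, comparison of means.** SE = √[1000 × (21.1 + 16.1)/(T × n)], and power = Φ(5/SE − 1.96) + Φ(−5/SE − 1.96). Example with T = 28, n = 142: SE = √(37,200/3,976) = 3.06 and power is 37%.

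| Per arm | 28 days | 10 days | 5 days |
|---|---|---|---|
| 142 | 37% | 16% | 11% |
| 236 | 56% | 24% | 14% |
| 250 | 58% | 25% | 15% |

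**4. The planned test.** Mann-Whitney power was simulated with Poisson counts at 236 per arm, 4,000 trials per setting. With fixed durations of 28, 10 and 5 days it was 52%, 22% and 13%. With exponential durations (mean parameter 10 and 5 days, limited to 1 to 28 days) it was 20% and 14%; with lognormal durations, 22% and 13%.

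**5. What 80% power would need.** At 236 per arm the SD must be at most 5/(√(2/236) × 2.802) = 19.4. Using both arms' Poisson variances, each arm needs 7.849 × (0.0211 + 0.0161)/0.005² = 11,679 ventilator days, or 49.5 per patient at 236 per arm and 46.7 at 250.

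**6. Omitted components.** The 21.1 leaves out ventilator associated pneumonia (in the Section 12.4 endpoint) and skin tears (in the Section 1.0 composite). At an assumed total of 30 per 1,000 the Poisson SD is 32.7 at 28 days and 54.8 at 10. Power for a fall of 5 at 236 per arm is then 41%, 18% and 11% at 28, 10 and 5 days.

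**7. A floor that does not assume Poisson.** If no patient has more than L ventilator days, a rate is either 0 or at least 1000/L. For mean m the variance is then at least (1000/L) × m − m².
- L = 28, m = 21.1: 35.7 × 21.1 − 21.1² = 308.4, SD 17.6 (17.8 at m = 16.1). Power is at most 66% at 142 per arm, 87% at 236 and 89% at 250.
- L = 25: SD 20.0 and 19.6 in the two arms; at most 78% at 236 per arm and 81% at 250.
- L = 10: SD 40.8 and 36.8; at most 29% at 236 per arm.

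At L = 28 the floor is reached only if 21.1/35.7 = 59% of control patients have exactly one event in exactly 28 ventilator days and the rest have none. This floor no longer excludes an SD of 15 if exposure can exceed about 31.5 days or the mean exceeds about 27.5.

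**The case against.** **The durations and the Poisson model are not in the documents.** True, and both are assumptions here. But no duration from 5 to 28 days reaches 80% at 500 patients under Poisson variation, and the plan offers no exposure figure of its own.

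**Poisson is not a lower bound.** This stands. Overdispersion would raise the SD, but counting at most one event per patient, a plausible reading of the Section 1.0 composite, lowers it. With that model and a common exposure, simulated Mann-Whitney power at 236 per arm is 86% at 28 days, 77% at 25 and 29% at 10. So 500 patients could suffice if nearly everyone were ventilated for about four weeks. At shorter exposures the shortfall does not depend on Poisson.

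**The 28-day limit is not stated for this endpoint.** Also true. Section 14.0 says "Patients will be followed after enrollment for 28 days or until hospital discharge, whichever occurs first", but Section 1.0 runs the endpoint "from the time of randomization to the earlier of death or 48 hours after extubation", and Section 8.0 collects events between "randomization and the earlier of death, hospital discharge, tracheostomy placement, or 48 hours after extubation". The 28-day floor is therefore conditional; the Poisson SDs at given durations are not affected.

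**The trial plans 500, not 284.** The larger number helps, but it looks ample only if the SD is accepted: with SD 15, 236 per arm would have 95% power. Nor does the stated dropout lead to it, since 284/0.944 gives 301.

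**The yes/no composite may be the real primary endpoint.** Then these rate-based figures do not apply, but neither does the 80% in Section 12.1, and the primary endpoint has no power statement at all.

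**Conclusion.** The concern holds. An SD of 15 is not credible as a between-patient value at plausible ventilation times, and the stated 80% power is not supported. At 142 per arm, power under Poisson variation is 11% to 37% over 5 to 28 ventilator days. It stays at or below about 66% even at the smallest variance possible, if exposure is capped at 28 days and the mean is 21.1.

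At the planned 500 less dropout, power under Poisson variation is 14% to 56% for a comparison of means and about 13% to 52% for the planned test. The result at 500 is model-dependent only near 28 days of exposure. If no patient exceeded 10 ventilator days, power could not pass about 29% for a comparison of means under any distribution with these mean rates.

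**What to change.** Remove the SD 15 calculation and the claim of 80% power for 5 per 1,000, and keep 500 patients. Reconcile the primary endpoint between Sections 1.0 and 12.4, and state whether day 28 closes its window. Then restate power or the detectable difference for the endpoint kept.

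- **If a rate is kept:** give expected ventilator days and a source for every component rate, use a count-based variance, and say that 500 patients are unlikely to give 80% power for 5 per 1,000 at plausible ventilation times. From 21.1, solving (21.1 − r)/√[1000 × (21.1 + r)/(236 × T)] = 2.802, 236 per arm detect with 80% power a fall to 14.6 (28 days), 10.8 (10 days) or 7.3 (5 days).
- **If the yes/no composite is kept:** state the assumed control risk and its source. By the pooled two-proportion formula, 236 per arm detect with 80% power 10% versus 3.5%, 20% versus 10.7%, or 30% versus 18.9%. These control risks are illustrative only.

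The cost is a change of text with no extra patients. The stated power becomes less favourable.

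### Section 12.1: a need of 142 per arm, an enrolment of 500 and a 5.6% loss allowance cannot all be right

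*Combined protocol and SAP*

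**What the plan says.** All three figures stand in section 12.1 of the combined protocol and SAP. The calculation takes "a standard deviation of 15 per 1000 ventilator days" and aims "to detect a clinically meaningful change of 5 episodes per 1000 ventilator days" "with 80% power at a two-sided alpha level of 0.05". From this it concludes: "we calculated a need for 142 patients in each arm". Allocation is 1:1 (section 1.0, Randomization), so the requirement is 284 patients in total. The next sentence sets the target: "We plan to enroll 500 patients which would allow for a 5.6% dropout or loss to follow-up rate".

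No other section gives an enrolment number, a second power target, an interim analysis or a further inflation factor. Section 6.5 says only that the list of assignments will be longer than the planned enrolment.

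**The concern.** A loss allowance should link the number needed for analysis to the number enrolled. Here it does not: any two of the three figures contradict the third, and the gap is about 200 patients, far more than rounding can explain.

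What is at stake is the traceability of the sample size. 500 is the only enrolment target in the documents, but section 12.1 gives no basis for it that agrees with its own figures. A reader cannot tell whether the design needs about 300 patients or 500, or whether the intended evaluable number is 142 or 236 per arm. If recruitment stopped between 300 and 500, the team could not say from section 12.1 whether the requirement had been met. The protocol also requests a waiver of informed consent (section 6.4), which is a further reason for the number enrolled to have a clear justification.

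**Working it through.** **Inputs.** From section 12.1: difference 5 and SD 15, both per 1,000 ventilator days; power 80%; two-sided alpha 0.05; 142 per arm; 500 enrolled; 5.6% loss. From section 1.0: 1:1 allocation. The summed rate of 21.1 per 1,000 ventilator days does not enter a two-means formula.

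**The plan's own figure.** For two means with equal arms:

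n per arm = 2 × (z for alpha + z for power)² × (SD/difference)² = 2 × (1.960 + 0.8416)² × (15/5)² = 141.3, rounded up to 142.

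The total is 284. A noncentral t calculation gives 79.9% power at 142 per arm. The 142 is therefore reproduced, and the fault lies in the step that follows.

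**The three figures, two at a time.**

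| Held fixed | Calculation | Result | Plan says |
|---|---|---|---|
| 142 per arm, 5.6% loss | 284 / (1 − 0.056) = 300.8 | 301 enrolled | 500 |
| 142 per arm, 500 enrolled | (500 − 284) / 500 = 216 / 500 | 43.2% loss tolerated | 5.6% |
| 500 enrolled, 5.6% loss | 500 × 0.056 = 28 lost; 472 / 2 | 236 per arm | 142 |

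Rounding conventions do not matter. Inflating each arm separately gives 142 / 0.944 = 150.4, so 151 per arm and 302 in total. Multiplying up instead gives 284 × 1.056 = 299.9, so 300. If 5.6% is itself rounded from anywhere between 5.55% and 5.65%, the third row moves only between 235.9 and 236.1 per arm.

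**Power at 236 per arm.** With difference 5 and SD 15 it is about 95% (95.2% by the normal formula, 95.1% by noncentral t), against the stated 80%.

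**Could another basis explain 500?**

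- *A different power.* 90% power needs 190 per arm: 380 / 0.944 = 402.5, so 403 enrolled. 95% power needs 234 per arm: 468 / 0.944 = 495.8, so 496. The latter is close to 500, but the plan states 80% and nowhere mentions 95%.
- *The Mann-Whitney test planned in section 12.4.* Assume an asymptotic efficiency relative to the t-test of 0.955 (normal data) or 0.864 (worst case for a pure shift). Then 142 / 0.955 = 148.7, so 149 per arm, and 298 / 0.944 = 315.7, so 316 enrolled. At the worst case, 142 / 0.864 = 164.4, so 165 per arm, and 330 / 0.944 = 349.6, so 350 enrolled. Neither approaches 500. These efficiencies are not in the documents and apply to shifts of a continuous distribution.

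**Which figure might be stale?** Two readings fit, and the documents confirm neither. 5.6% fits a total of about 300 if the need was 142 per arm (300 / 284 = 1.056). It fits 500 if the need was 236 per arm.

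**The case against.** The strongest reply is that 500 exceeds every number the calculation requires, so nothing is lost. Read literally, 500 does allow for 5.6% loss, and for much more. No analysis in sections 12.2 to 12.6 uses 284 or 5.6%. Much of this stands: no loss of validity and no harm to participants is shown. But a loss allowance given to one decimal place reads as the allowance the target was built on, and against 284 it is wrong by a wide margin.

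A second point also stands. The discrepancy is conservative only if 142 and 500 are both correct. If the true need was 236 per arm, or the true target about 300, there is no surplus.

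Third, the Mann-Whitney check is limited. At about 21 events per 1,000 ventilator days many patients may have a rate of zero, and with heavy ties the efficiencies used above need not bound the inflation. The check therefore rules out that explanation only under a shift model. The inconsistency does not depend on it, and section 12.1 does not claim that 500 came from such an adjustment.

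Finally, writing about 43% into the protocol would state what 500 tolerates, not what loss anyone expects. That is a fair caution about how the correction is worded.

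**Conclusion.** The concern holds, with high confidence, and should be fixed. The need of 142 per arm is correct for its inputs, but it does not agree with 500 enrolled and 5.6% loss. The size is about 301 versus 500 enrolled, 43.2% versus 5.6% loss tolerated (216 versus 28 patients), or 236 versus 142 evaluable per arm (94 more).

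These results use only the plan's figures and 1:1 allocation. The direction is conservative for power if 142 and 500 both stand. The 95% power at 236 per arm is conditional on difference 5, SD 15 and the two-means model. It is not the power of the planned Mann-Whitney analysis and gives no assurance for the primary endpoint. The error is in the stated basis of the sample size, and the documents do not show which figure caused it.

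**What to change.** Reconcile the three figures in section 12.1. The sponsor should first check the sample-size records for the stale one. If 500 is kept, there are two ways to correct the sentence:

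- replace the 5.6% statement with the loss that 500 tolerates against 284 (about 43%), worded as a tolerance and not as an expected loss; or
- state that 5.6% loss leaves 236 evaluable patients per arm.

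In either case, give the actual basis for 500. Do not choose a new SD, difference or power after the fact so that the formula returns 500.

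Do not reduce enrolment on this arithmetic alone. The calculation adds only the dislodgement and lip ulcer rates ("Using the sum of these overall incidences of 21.1 per 1000 ventilator days"). The primary endpoint in section 1.0 is a "Composite of any of: presence of lip ulcer, endotracheal tube dislodgement, or facial skin tears", and section 12.4 analyses "incidences of lip ulcers, tube dislodgement, or ventilator associated pneumonia per 1,000 ventilator days". Aligning the calculation with the primary endpoint is a separate issue and comes before any change of target.

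The cost is a text correction in section 12.1 with enrolment unchanged. If the sponsor finds that 500 or 142 is itself wrong, changing the target is a design change that needs a protocol amendment and goes beyond this correction.
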